7.0 Participant Disposition

The number and percentage of participants in each of the 3 study populations (Safety and ITT and mITT) will be summarized by treatment group and study center; the number of participants screened will be summarized overall only by study center.

Screen-failure participants (ie, participant who consent to participate in the clinical study but not randomized) and the associated reasons for failure to randomize will be tabulated for the screening period, the run-in period and overall for the Screened Population. The number and percentage of participants rolled over to study RLM-MD-04 will be also be tabulated for all the participants in the Screened Population who were screen-failed during the run-in period.

The number and percentage of participants who complete the double-blind treatment period and of participants who prematurely discontinue during the same period will be presented for each treatment group and pooled across treatment groups for the ITT Population. The reasons for premature discontinuation from the double-blind treatment period as recorded on the termination pages of the electronic case report forms will be summarized (number and percentage) by treatment group for the ITT Population. All participants who prematurely discontinue during the double-blind period will be listed by discontinuation reason for the ITT Population.

8.0

Demographics and Other Baseline Characteristics

Demographic parameters (eg, age, race, ethnicity, sex) and other baseline characteristics (weight, BMI) will be summarized in total and by treatment group for the Safety and ITT Populations.

Abnormalities in participants' medical and surgical histories will be coded using the *Medical Dictionary for Regulatory Activities*, version 21.1 or newer. The number and percentage of participants with abnormalities in medical and surgical histories in each system organ class and preferred term will be summarized by treatment group for the Safety Population. Diabetic gastroparesis and diabetes mellitus history and history of diabetes gastroparesis symptoms will also be summarized by treatment group for the Safety Population.

Prior medication is defined as any medication started before the date of the first dose of double-blind study treatment. *Concomitant medication* is defined as any medication taken on or after the date of the first dose of double-blind study treatment. Any prior medications started more than 30 days before the date of the first dose of double-blind study treatment and any concomitant medications started after the date of the last dose of double-blind study treatment will not be presented in the summary tables, but will be included in the participant data listings.

Both prior and concomitant medication use will be summarized by the number and proportion of participants in each treatment group for the Safety Population. The *WHO Drug Dictionary*, Version B2 March 2017 or newer, will be used to classify prior and concomitant medications by WHO Drug Anatomical/Therapeutic/Chemical category and drug preferred name. Multiple medications used by a participant will only be counted once for the coded drug preferred name or therapeutic class.

9.0

Extent of Exposure and Treatment Compliance

9.1

Extent of Exposure

Exposure to the study treatment for the Safety Population during the double-blind treatment period will be summarized for treatment duration, calculated from the eDiary as the number of days from the date of the first dose of study treatment to the date of the last dose of study treatment, inclusive. Descriptive statistics (number of participants, mean, SD, median, Q1, Q3, minimum, and maximum) will be presented by treatment group. The date of first dose is the date of randomization(date of baseline visit).

Patient-years, defined as duration of exposure to the study treatment in years, will be summarized by treatment for the Safety Population.

9.2

Measurement of Treatment Compliance

Dosing compliance for a specified period is defined as the number of injections actually taken by a participant during that period divided by the number of injections expected for the same period multiplied by 100. The number of injections actually taken is obtained from the participants' responses in the item of 'How many injections of study medication have you administered today?' from the electronic hand-held device. The number of injections expected during a period is the number of days in the period multiplied by 2.

Descriptive statistics for study drug compliance will be presented by treatment group for each treatment week, for the last 6-week treatment period (i.e., Week 7-12) and for the whole double-blind treatment period (ie, Week 1-12), based on the Safety Population. Weeks are defined relative to randomization day as described in Section [16.0](#).

10.0 Efficacy Analyses

The efficacy analyses will be based on the mITT Population.

Most efficacy parameters will be derived from the DGSSD, a 7-item, patient-reported daily diary designed to assess the severity of 6 core signs and symptoms of DG—nausea, abdominal pain, postprandial fullness, bloating, vomiting, and early satiety—and the frequency of vomiting episodes (Appendix 1). For purposes of the analyses, weekly values will be calculated from the daily e-diary data as described in Section 16.3 of this SAP. For weeks with less than 4 days of available DGSSD data, weekly values will be set to missing.

Baseline values for parameters are derived from the DGSSD collected in the Run-in period, (ie, *Diabetic Gastroparesis Symptom Severity Score (DGSSS: sum of nausea, abdominal pain, postprandial fullness, and bloating), nausea, abdominal pain, postprandial fullness, bloating, early satiety, vomiting frequency and vomiting severity*) following the steps below:

- Weekly value for Week -2 and Week -1 will be the average value of DGSSD in the week (See the analysis week definition for Week -2 and Week -1 in Section 16.2.1);
- Baseline will be the average of the two weekly values of Week -2 and Week -1.

All statistical tests will be 2-sided hypothesis tests performed at the 5% level of significance for main effects. All confidence intervals will be 2-sided 95% confidence interval, unless stated otherwise.

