10.1 Primary Efficacy Parameters

There are two primary efficacy parameters in each study as follows:

- a) **Change from Baseline to Week 12 in the weekly DGSSS:** Baseline is the average of the 2 weekly DGSSS from the 2-week, placebo Run-in Period.
- b) **Vomiting Study Responder (V-SR):** A Vomiting Study Responder is defined as a participant with zero weekly vomiting episodes during each of the last 6 weeks of the 12-week Treatment Period.

In this study, the primary efficacy analysis (see Section 10.1.1 below) is said to have achieved the primary study objective if it indicates that relamorelin is superior to placebo for testing on at least one of the two primary efficacy parameters (following the specified multiplicity testing procedure as described in Section 10.3).

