10.1.1.2 Vomiting Study Responder (V-SR)

For the primary efficacy responder parameter V-SR, the proportion of responders in the RLM group and the placebo group will be analyzed by the Cochran-Mantel-Haenszel (CMH) test controlling for geographic region. The number, percentage, and the 95% confidence interval for the percentage of Responders by treatment group, the difference in responder rates between the RLM and the placebo group and its corresponding 95% confidence interval, and the 2-sided p-value associated with the above CMH test will be presented. The Mantel-Haenszel estimate of odds ratio (RLM divided by Placebo) - controlling for geographic region- and the corresponding 95% confidence interval will also be provided.

A participant will be considered a vomiting study non-Responder (ie not a V-SR) if the weekly number of vomiting episodes is missing for any of the last 6 weeks of the 12-week Treatment Period.

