10.1.2 Sensitivity Analysis for Missing data

Missing weekly DGSSS and missing number of weekly vomiting episodes will be imputed using multiple imputation (MI) approaches. MI will be performed under Missing at Random (MAR) and Missing not at random (MNAR) assumptions using the SAS/STAT procedures PROC MI and PROC MIANALYZE.

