10.1.2.1 Sensitivity Analysis for Missing Data of Vomiting Study Responder

MI for V-SR will be performed under both MAR and MNAR assumptions. We will follow the steps below to generate datasets and analyze the data:

1. Imputed datasets generation
 - a) Missing at Random (MAR): The imputation of post baseline weekly values will be based on a multivariate normal distribution. In each imputation, a Monte-Carlo Markov chain (MCMC) method will be used to impute the missing values of post baseline weekly values from the observed data of the same group. The initial mean vector and covariance matrix for the MCMC will be obtained using an expectation–maximization algorithm.
 - b) Missing not at random (MNAR): The implementation of the pattern-mixture model with control-based pattern imputation of Ratitch and O’Kelly (2011) will be used to impute missing data under the MNAR assumption.
 - o Intermittent (non-monotone) missing data in both treatment groups are imputed using the MCMC method under the MAR assumption as described in Step 1- a.
 - o remaining monotone missing data are imputed using a pattern-mixture model approach using a sequential regression imputation model estimated based on data from the placebo arm only.

Imputed values for the number of weekly vomiting episodes will be restricted to ≥ 0 post imputation. 50 imputed datasets will be generated.

2. Calculate V-SR rate in the imputed datasets.
3. Model-based key estimates (odds ratio and standard error) will be obtained for V-SR for each imputed dataset using the same method as described in Section 10.1.1.2.
4. Take the log transformation for odds ratio ($\log(OR)$) and calculate standard error of transformed estimate ($SE(\log(OR))$) in each imputed dataset. $SE(\log(OR))$ is obtained from the log-transformed lower and upper confidence limits for the odds ratio estimate.
5. Output the combined $\log(OR)$, $SE(\log(OR))$, and p-values for all imputed datasets using PROC MIANALYZE.
6. Back transform the combined results of OR and SE and calculate 95% CI, by taking the exponentiation of the point estimates for $\log(OR)$ and for the lower and upper CI limits for $\log(OR)$ (Ratitch et al. ,2013).

10.1.2.2 Sensitivity Analysis for Missing Data of Change from Baseline in the Weekly DGSSS

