16.2 Analysis Weeks and Visit Time Windows for Efficacy Analysis

16.2.1 Analysis Weeks for Efficacy Analysis

Table 16.2.1-1 below presents the analysis weeks assigned for the efficacy analysis of the participant daily diary data related to DGSSD. These analysis weeks will be used in the calculations for all week-based endpoints (eg, weekly DGSSS, weekly vomiting frequency, individual symptoms weekly scores etc.).

Table 16.2.1-1. Analysis Time Windows for Efficacy Analysis

Period	Analysis Week	Begins^a	Ends^a
Pretreatment (Baseline ^b)	Week -2	Day -14	Day -8
	Week -1	Day -7	Day -1
Treatment	Week 1	Day 1, day of randomization	Day 7
	Week 2	Day 8	Day 14
	Week 3	Day 15	Day 21
	Week 4	Day 22	Day 28
	Week 5	Day 29	Day 35
	Week 6	Day 36	Day 42
	Week 7	Day 43	Day 49
	Week 8	Day 50	Day 56
	Week 9	Day 57	Day 63
	Week 10	Day 64	Day 70
	Week 11	Day 71	Day 77
	Week 12	Day 78	Day 84

[figure not shown]
a Relative to the date of randomization; Day 1 = the day of randomization.

[figure not shown]
b Baseline values for efficacy parameters will be derived as average of the two pretreatment weeks.

[figure not shown]
For the Treatment Period, diary day is calculated as (diary date - date of randomization + 1). For the Pretreatment Period, diary day is calculated as (diary date - date of randomization).

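### The multiple-imputation analyses of Vomiting Study Responder can score as a responder someone whose diary already records vomiting in Weeks 7-12

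*SAP*

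**What the plan says.** - **Short weeks.** SAP 10.0: "For weeks with less than 4 days of available DGSSD data, weekly values will be set to missing". SAP 16.2.1 applies one set of analysis weeks to every weekly endpoint, and its examples include weekly vomiting frequency. Weeks 7-12 run from Day 43 to Day 84.
- **Endpoint.** SAP 10.1, on who counts as a responder: "participant with zero weekly vomiting episodes during each of the last 6 weeks of the 12-week Treatment Period".
- **Primary analysis.** SAP 10.1.1.2 scores a participant as a non-responder "if the weekly number of vomiting episodes is missing for any of the last 6 weeks of the 12-week Treatment Period".
- **Sensitivity analyses.** SAP 10.1.2: "Missing weekly DGSSS and missing number of weekly vomiting episodes will be imputed using multiple imputation (MI) approaches". For vomiting this is done twice. The MAR analysis draws from a multivariate normal distribution. The MNAR analysis fills intermittent gaps in the same way and monotone gaps from a placebo-based sequential regression. The only limit stated for imputed vomiting counts is that they may not be negative. Step 2 of SAP 10.1.2.1 is then: "Calculate V-SR rate in the imputed datasets".
- **Status.** SAP 4.0 reports termination on 04 September 2020. It says the full planned analyses no longer apply, and that amendment 2 adds descriptive efficacy summaries.

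**The concern.** A minimum of 4 diary days suits an average symptom score, where a short week gives only an imprecise mean. It does not suit an endpoint that fails on one event. If a participant makes three entries in Week 9 and one of them records vomiting, the week cannot be a zero week, whatever happened on the other four days.

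MAR and MNAR are assumptions about data that were not seen. Once the recorded episode is set aside and the week is drawn from a model, the analysis varies something that was seen. It then no longer tests only the missing-data assumption on the primary endpoint, and it departs from the endpoint definition in SAP 10.1. What is at stake is the fidelity of two supporting analyses, not the primary result.

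**Working it through.** **The plan's own figure.** SAP 14.0 claims more than 90% power for at least one primary hypothesis with about 300 per arm. For vomiting alone (26% vs 11%, two-sided alpha 0.025, the first critical value in SAP 10.3), a two-proportion calculation gives 99.4% with 300 per arm and 97.9% with 240 (20% dropout). The claim is met on this endpoint and is not in dispute. The DGSSS simulation cannot be rerun because Table 14-1 is not in the text available.

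**One participant followed through the rules.** Five of Weeks 7-12 are complete with zero episodes. The sixth has 3 diary days and 2 recorded episodes.

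1. SAP 10.0: 3 days is fewer than 4, so the sixth week is missing.
2. SAP 10.1.1.2: a week is missing, so the primary analysis scores a non-responder. This agrees with the diary.
3. SAP 10.1.2.1, step 1: the week is drawn from a model. A draw at or below 0 becomes 0.
4. SAP 10.1.2.1, step 2: six zero weeks, so a responder. This contradicts the diary.

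For one missing week under the normal model, P(draw ≤ 0) = Φ(−mean/SD), using the conditional mean and SD:

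| mean/SD | 0 | 0.25 | 0.5 | 0.75 | 1.0 |
|---|---|---|---|---|---|
| P(scored zero) | 50% | 40% | 31% | 23% | 16% |

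**Size without dropout (illustrative).** The documents give neither the frequency of 1-3 day weeks nor the weekly count distribution, so both are assumed. Counts are gamma-Poisson with mean m per week and frailty shape k of 0.5 or 1, calibrated by (1 + 6m/k)^(−k) = 11% or 26%. The chance that a week in Weeks 7-12 has only 1-3 diary days is 2%, 5% or 10%. Draws are multivariate normal under MAR, floored at 0, with mean and covariance taken from the complete simulated data. Expected number wrongly scored as responders, per 300, per imputed dataset:

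| Response | k | 2% | 5% | 10% |
|---|---|---|---|---|
| 11% | 0.5 | 0.07 | 0.12 | 0.27 |
| 11% | 1.0 | 0.12 | 0.18 | 0.31 |
| 26% | 0.5 | 0.08 | 0.27 | 0.54 |
| 26% | 1.0 | 0.19 | 0.36 | 0.58 |

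On an arm's response rate this is 0.07/300 = 0.02 to 0.58/300 = 0.19 percentage points. The numbers are small because most participants who vomit in a short week also vomit in a valid one. Between 4.2 and 77.8 per 300 have a recorded episode in a short week, but only 0.15 to 2.33 have zeros in all their other available weeks. Of those, 25-45% are scored as responders in a given imputation. With the same k and short-week rate in both arms, the largest gap between arms is 0.58 − 0.31 = 0.27 participants, or 0.27/300 = 0.09 points. The assumed treatment difference is 26 − 11 = 15 points.

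**Size with dropout (illustrative).** The assumptions are 20% dropout spread evenly, 85-92% diary completion and no rise in vomiting before exit. About 1 (relamorelin) and 2 (placebo) per 300 have a status that depends on imputation although an episode is already recorded. The chance that all missing weeks are imputed as zero is 3-19% with flooring and 4-32% with rounding. That gives 1 × 0.03 = 0.03 to 2 × 0.32 = 0.64 participants per arm per dataset, again below one. One participant in 300 is 0.33 points, which serves as a rounded upper limit.

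**The case against.** **Unseen text.** SAP 10.0 refers to Section 16.3 for the weekly calculations, and that section is not in the text available. It could contain a rule for short weeks with a recorded episode. This stands as a caveat. Against it, SAP 10.0 states the 4-day rule without qualification.

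**Meaning of the lower bound.** If negative draws were redrawn instead of set to 0, exact zeros would practically never occur without rounding, and no rounding rule is visible. Flooring is the more natural reading. The proposed sentence works under either.

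**Consequence.** The multiplicity procedure in SAP 10.3 does not use the imputation analyses. The primary analysis scores these participants correctly, and the rescue-medication repeat in SAP 10.6 also treats missing weeks as non-response. After termination the full analyses are not planned. All of this stands, and it sets the severity.

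**A stronger reading to avoid.** A reader might infer that vomiting peaks just before a participant leaves, so that many failures are lost in the last short week. Such weeks are foreseeable. Stopping treatment means leaving the study (Protocol 8 and 8.1), and if 60 of 300 leave evenly over 84 days, 60 × 42/84 = 30 leave in Weeks 7-12 and 30 × 3/7 ≈ 13 have a final week of 1-3 days. That is the number exposed, not the number misclassified. Nothing in the documents shows a rise in vomiting before exit, and SAP 14.0 plans on MCAR dropout. With an invented 50% daily chance of an extra episode in the last 3 days, up to 7 in the relamorelin arm would have a recorded episode set aside. At the no-surge conversion rates of 19% (flooring) and 32% (rounding) that would be 7 × 0.19 = 1.3 to 7 × 0.32 = 2.2 participants, but the surge has no source. Early exit also leaves whole weeks missing afterwards, and these must all be imputed as zero too, which makes misclassification less likely.

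**Conclusion.** The point holds for the two imputation analyses of Vomiting Study Responder and for nothing else. As written, SAP 10.0 and 10.1.2.1 together let a model draw replace an observed failure. That is a classification error, not a matter of preference.

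The size is about one participant per arm per imputed dataset or fewer, roughly 0.02-0.3 percentage points. This rests on assumed diary completion, dropout and count distributions, on flooring (or rounding) to zero, and on no rule to the contrary in Section 16.3. It is a range under assumptions, not an estimate.

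The documents do not support reading this as a threat to the primary vomiting result, as a material bias in favour of relamorelin, or as evidence that vomiting rises before dropout. Severity is low.

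**What to change.** Add to SAP 10.1.2.1, step 2:

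> *A participant with any recorded vomiting episode on any diary day from Day 43 to Day 84, including days in weeks set to missing, is a non-responder in every imputed dataset.*

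If Section 16.3 already says this, a cross-reference is enough. The sentence covers both the MAR and the MNAR analysis and adds no modelling assumption. It brings the chance that such a participant is scored a responder to 0. The cost is one line of code and slightly lower response rates in the imputation analyses. The primary analysis, sample size and power do not change. Because this SAP also governs RLM-MD-01, the sentence would apply there too.

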10.1 Primary Efficacy Parameters

There are two primary efficacy parameters in each study as follows:

- a) **Change from Baseline to Week 12 in the weekly DGSSS:** Baseline is the average of the 2 weekly DGSSS from the 2-week, placebo Run-in Period.
- b) **Vomiting Study Responder (V-SR):** A Vomiting Study Responder is defined as a participant with zero weekly vomiting episodes during each of the last 6 weeks of the 12-week Treatment Period.

In this study, the primary efficacy analysis (see Section 10.1.1 below) is said to have achieved the primary study objective if it indicates that relamorelin is superior to placebo for testing on at least one of the two primary efficacy parameters (following the specified multiplicity testing procedure as described in Section 10.3).

10.1.1 Primary Analysis

10.1.1.1 Change from Baseline to Week 12 in the Weekly DGSSS

The primary efficacy parameter, the change from baseline to Week 12 in the weekly DGSSS, will be analyzed using a longitudinal, mixed-effects model with repeated measures (MMRM) approach.

The MMRM model will include fixed effects for geographic region, treatment, week, treatment-by-week interaction, as well as baseline and baseline-by-week interaction values as the covariates with unstructured variance-covariance matrix being common to all participants for the repeated measures over weeks. In case the model will not converge with the unstructured covariance structure, the Toeplitz structure (TOEP) will be used instead. Least square (LS) mean changes from baseline for each treatment group, and LS mean difference between RLM group and placebo group, and the associated 95% confidence interval for the difference will be provided, along with the reported p-values (two-sided).

In addition, cumulative distribution function plot will be presented for the change from baseline to Week 12 in the Weekly DGSSS for each treatment group.

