The study was early/prematurely terminated on 04 September 2020 when the letter explaining termination activities was sent to all investigators. As a result, the original planned full analyses for the study are no longer applicable for the terminated study. Only abbreviated clinical study report (aCSR) for RLM-MD-01 and RLM-MD-02 will be developed.

The statistical analysis plan (SAP) amendment 2 is based on the amendment #1 SAP dated 29 Sep 2020. The major change to the amendment #1 SAP is to add descriptive analyses for the primary and secondary efficacy endpoints for the results posting on ClinicalTrials.gov and EudraCT (European Union Drug Regulating Authorities Clinical Trials Database) and add the COVID-19 data listing. Please refer to Section [19.2](#) Appendix 2 for details of the outlined analyses for the aCSR.

4.1 **Study Design**

Studies RLM-MD-01 and RLM-MD-02 are identical, designed as global, multicenter, randomized, double-blind, placebo-controlled, parallel-group in participants with diabetic gastroparesis.

In each study, approximately 600 eligible participants will be randomly assigned in a ratio of 1:1 to 1 of 2 treatment groups as follows:

[figure not shown]
- Treatment Group 1: Relamorelin (RLM) 10 µg BID (n=300)
- Treatment Group 2: Placebo BID (n=300)

The duration of each study is 18 weeks, including a 4-week Screening Period, a 2-week single blind Run-in Period, and a 12-week Treatment Period:

[figure not shown]
- Run-in Period: Participants who meet initial study entry criteria during the Screening Period will enter a 2-week Run-in Period, during which they will self-administer single-blind placebo twice daily subcutaneously. Using an electronic hand-held device, participants will report their daily symptoms via the Diabetic Gastroparesis Symptom Severity Diary (DGSSD) as well as their overall global impression of status, treatment satisfaction, treatment compliance, and use of rescue medication.
- 12-week Treatment Period: Participants who meet study entry criteria at the end of the Run-in Period, will be randomized 1:1 to blinded treatment with relamorelin 10 µg or placebo, and will continue to use the electronic hand-held device for reporting of their symptoms via the DGSSD as well as their overall global impression of status and change, treatment satisfaction, compliance, and use of rescue medication.

[figure not shown]

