MMRM analysis of change from baseline in the weekly DGSSS is based on the assumption of MAR and this approach uses available data including data from participants with partial data to estimate the mean treatment effect without filling in the missing data (Mallinchrod et al., 2008). Thus, MI for change from baseline in the weekly DGSSS will be performed only under MNAR assumption. The following steps will be followed to generate datasets and analyze the data:

1. Imputed datasets generation: Use the method as described in Step 1 Part b) in Section 10.1.2.1 to generate 50 datasets. Imputed values for change from baseline in the weekly DGSSS will be restricted to ≥ -40 and ≤ 40 .
2. Model based key estimates (LSMean difference between treatment group and standard error) will be obtained for the change from baseline to week 12 in the weekly DGSSS for each imputed dataset using the same method as described in Section 10.1.1.1.
3. Calculation of the combined mean difference, 95% CI, and p-value for the change from baseline to week 12 in the weekly DGSSS will be done using the method proposed by Rubin (1987) via PROC MIANALYZE.

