10.3 Multiple Comparisons Procedure

[figure not shown]
The overall study Type 1 error will be controlled for the 6 efficacy parameters, 2 primary and 4 secondary parameters, as defined above (Sections 10.1 and 10.2). To control the overall type-1 error rate of the study, the hypotheses of interest will be grouped into the following two families:

[figure not shown]
- Family 1:
 - Hypothesis H1: Comparison of relamorelin vs. placebo in change from baseline to Week 12 in the Weekly DGSSS
 - Hypothesis H2: Comparison of relamorelin vs. placebo in proportion of participants who achieved responder status for V-SR
- Family 2:
 - Hypotheses H3-H6: Comparison of relamorelin vs. placebo in the response rates of the individual symptoms comprising DGSSS (ie, nausea, abdominal pain, bloating and postprandial fullness)

[figure not shown]
Then, multiple testing will be performed in two steps ([Dmitrienko et. al., 2008](#)) as follows:

- Step 1: Treatment comparisons to placebo in change from baseline to Week 12 in the Weekly DGSSS and vomiting response rates will be performed using the truncated Holm test at alpha=0.05. A truncation parameter of 0.5 will be used. According to this procedure, the smallest and largest p-values will be compared to the critical values of 0.025 and 0.0375 respectively in a step-down manner (i.e. starting with the smallest p-value and stopping the testing with the first non-rejected hypothesis).
- Step 2: If any of the comparisons at Step 1 is significant, the treatment comparisons to placebo in the individual symptoms response rates will be performed using the regular Holm test at a level alpha that depends on the unused alpha from Step 1 as follows:
 - 1) If both H1 and H2 are both rejected in Step 1, H3-H6 will be tested using an overall alpha=0.05
 - 2) If only one of H1 and H2 is rejected in Step 1, H3-H6 will be tested using an overall alpha=0.0125
 - 3) If none of H1 and H2 is rejected, the testing procedure will be stopped and H3-H6 are not tested

According to the above procedure, the k-th ordered p-value in 1) and 2) in Step 2 will be compared to the critical values of $\alpha/(4-k+1)$, $k=1, \dots, 4$, in a step-down manner (i.e. starting with the smallest p-value and stopping the testing with the first non-rejected hypothesis), where α is the significance level from Step 2.

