14.0 Determination of Sample Size

The sample size and statistical power for the DGSSS endpoint was assessed by simulation. Data were simulated for the DGSS over time under the assumption of a multivariate normal distribution and based on mean responses in Study RM-131-009 variance -covariance structure ([Table 14-1](#)). A missing completely at random (MCAR) dropout rate of 20% by Week 12 was assumed for each treatment.

Vomiting response rates were assumed to be those observed in Study RM-131-009 (26% and 11% for treatment and placebo respectively). Sample size was assessed using the POWER procedure in SAS.

The sample size of approximately 300 participants per arm will provide more than 90% power to reject at least one of the primary null hypotheses using the multiplicity approach described in [Section 10.3](#).

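### If the unstructured MMRM fails, the only fallback (TOEP) assumes equal variance at every week, so the Week 12 standard error is too small if variance rises

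*SAP*

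**What the plan says.** SAP 10.1.1.1 analyses the weekly DGSSS change by MMRM with an "unstructured variance-covariance matrix being common to all participants for the repeated measures over weeks". The only provision for failure is: "In case the model will not converge with the unstructured covariance structure, the Toeplitz structure (TOEP) will be used instead". The supplied text gives no structure with week-specific variances, no ordered list of structures, and no statement of which standard error accompanies a structured fit. Protocol Table 10-2 describes the same model and names no covariance structure.

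The rule reaches beyond the main test. The MNAR analysis in SAP 10.1.2.2 re-uses the 10.1.1.1 method on each imputed dataset, and SAP 10.6 repeats the primary analyses with further weekly values set to missing after rescue medication.

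Under SAP 10.3, "the smallest and largest p-values will be compared to the critical values of 0.025 and 0.0375 respectively", and a rejection helps release alpha to the four symptom-responder hypotheses.

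SAP 14.0 says that the DGSSS simulation was "based on mean responses in Study RM-131-009 variance -covariance structure", citing Table 14-1. That table is not in the supplied text, so the week-by-week SDs are unknown here.

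**The concern.** A homogeneous Toeplitz matrix over 12 weeks has 12 parameters: one variance and 11 lag covariances. The unstructured matrix has 12 × 13 / 2 = 78. Reducing the number is the purpose of a fallback, but TOEP does so partly by forcing the Week 12 variance to equal a compromise across all weeks. H1 concerns Week 12 only, so an error in that one variance goes straight into its standard error, confidence interval and p-value.

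Rising variance is plausible, though not shown. Entry requires a run-in average DGSSS of at least 16, the model adjusts for baseline, and Week 1 directly follows the two weeks that form baseline. Early scores may therefore stay close to baseline and spread later. If so, a fallback analysis would test H1 above 0.025 or 0.0375 and could open the secondary family too easily.

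**Working it through.** **1. The plan's own figures.** The truncated Holm values with parameter 0.5 reproduce: 0.05 × (0.5/2 + 0.5/2) = 0.025 and 0.05 × (0.5/1 + 0.5/2) = 0.0375. The stated power of more than 90% to reject at least one primary hypothesis also holds, from vomiting alone. With 26% against 11%, 300 per arm and two-sided alpha 0.025, the pooled null SE is √(2 × 0.185 × 0.815 / 300) = 0.0317 and the alternative SE is √((0.26 × 0.74 + 0.11 × 0.89) / 300) = 0.0311. Power is Φ((0.15 − 2.241 × 0.0317) / 0.0311) = 99.4%. The DGSSS power cannot be reproduced without Table 14-1.

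**2. Mechanism with complete data.** The Week 12 difference is essentially unchanged under TOEP, but its model SE uses roughly the average variance. For an SD rising from 5 to 8 with correlation 0.6 + 0.4 × 0.7^lag, the fitted common SD is 6.597:

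- model SE = 6.597 × √(2/300) = 0.539
- true SE = 8 × √(2/300) = 0.653
- ratio = 0.825
- actual level = 2 × (1 − Φ(2.241 × 0.825)) = 0.065 at nominal 0.025

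A 20,000-trial simulation using the average variance gave 0.065. Using the Week 12 variance it gave 0.025.

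**3. With dropout.** From the SAP: 12 weeks, 300 per arm, and 20% missing completely at random by Week 12, taken as monotone. Assumed: the SD paths and four correlation shapes, namely AR(1) 0.8, AR(1) 0.9, compound symmetry 0.7, and a decay from 0.9 to a floor of 0.5. The TOEP matrix closest in likelihood to the true covariance was found, and level = 2 × (1 − Φ(z × model SE / true SE)), with z = 2.241 for 0.025 and 2.080 for 0.0375.

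| SD path | Ratio Week 12 / Week 1 | Level at 0.025 | Level at 0.0375 |
|---|---|---|---|
| Linear rise | 1.29 | 0.047–0.048 | 0.065–0.066 |
| Linear rise | 1.5 | 0.062–0.064 | 0.083–0.085 |
| Linear rise | 2.0 | 0.089–0.092 | 0.115–0.118 |
| Rise to Week 4, then flat | 1.29 | 0.032–0.036 | 0.046–0.052 |
| Rise to Week 4, then flat | 1.5 | 0.036–0.042 | 0.051–0.059 |
| Rise to Week 4, then flat | 2.0 | 0.042–0.049 | 0.059–0.068 |
| Flat | 1.0 | 0.025 | 0.0375 |
| Linear fall, 9 to 7 | 0.78 | 0.009–0.010 | about 0.016 |

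Worked case (AR(1) 0.9, SD 6 to 9, linear): 0.658 / 0.791 = 0.832, and 2.241 × 0.832 = 1.865, so the level is 0.062. The true SE under TOEP is only 0.0% to 1.3% above the unstructured SE, so the fault lies in the reported SE and not in precision.

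**4. Does a sandwich SE repair it?** In 23,000 simulated trials per case under MCAR dropout, with TOEP weights, the level at nominal 0.025 was:

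| Case | Model SE | Sandwich SE |
|---|---|---|
| AR(1) 0.9, SD 6 to 9 | 0.063 | 0.026 |
| Compound symmetry 0.7, SD 4.5 to 9 | 0.089 | 0.025 |
| Random slope, SD 5.0 to 8.3 | 0.078 | 0.026 |

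**5. Overall level.** With an assumed failure rate f, the overall level is (1 − f) × 0.025 + f × conditional level.

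- Lowest rising case (ratio 1.29, flat from Week 4, f = 1%): 0.99 × 0.025 + 0.01 × 0.032 = 0.0251.
- Highest rising case (ratio 2.0, linear, f = 5%): 0.95 × 0.025 + 0.05 × 0.0917 = 0.0283.
- Falling SD (9 to 7, f = 5%): 0.95 × 0.025 + 0.05 × 0.0095 = 0.0242.

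**The case against.** Three things must coincide: the unstructured fit fails, the residual variance rises, and the model-based SE is used. The documents establish none of them. The sponsor had the Phase 2b covariance and may have known the variance to be stable. Smaller SD ratios are as admissible as 1.5 or 2.0: at 1.10 the level is about 0.033 for a linear rise and 0.028 to 0.029 if flat from Week 4; at 1.05 it is about 0.029 and 0.026 to 0.027. The unconditional effect is small and can go either way. The SAP does fix its fallback in advance, so there is no after-the-fact choice of structure. Finally, SAP 4.0 states that "the original planned full analyses for the study are no longer applicable for the terminated study" and adds only descriptive efficacy summaries, so no H1 test remains to be distorted.

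All of this stands, and it sets the priority of the point. It does not show that the rule is sound when invoked. A fallback matters only in the case where it is used, and there a one-variance model with its own SE has no protection at the single week that is tested. The sentence also governs RLM-MD-01, which shares this SAP.

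**Conclusion.** The point holds as a minor weakness of the written plan. If TOEP is used with its model SE and the SD rises by a factor of 1.29 to 2.0, the test of H1 at nominal 0.025 runs at 0.032 to 0.092, depending on the size and shape of the rise. With a flat SD it is exact; with a falling SD it is conservative. The direction and the SDs are assumptions, because the covariance table is not in the supplied text. So are the 1% to 5% failure rates, under which the overall level lies between about 0.024 and 0.0283. Early termination means no practical effect on the descriptive efficacy results.

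**What to change.** Replace the fallback sentence in SAP 10.1.1.1 with:

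> If the unstructured model does not converge, heterogeneous Toeplitz (TOEPH) will be used, then TOEP; with either, the standard error, confidence interval and p-value will use the empirical (sandwich) estimator.

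The minimum change is to keep TOEP and add the sandwich SE, which alone restores the level under MCAR dropout. TOEPH with its model SE alone is only a partial repair when the correlation is not Toeplitz: 0.034 to 0.048, against 0.051 to 0.077 for TOEP, under six random-slope covariances.

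TOEPH should come first because, as SAP 10.1.2.2 notes, "MMRM analysis of change from baseline in the weekly DGSSS is based on the assumption of MAR", and a sandwich SE does not remove bias from a wrong covariance. That gain is conditional. If dropout depends on the last score in one arm only and the SD rises, TOEP biases the Week 12 difference by 0.04 to 0.36 points (true SE 0.71 to 0.79). TOEPH removes this when the correlation is Toeplitz, and cuts it from 0.36 to 0.25 in the random-slope case. One-arm dependence is an assumption; SAP 14.0 plans on MCAR dropout in both arms. If dropout works alike in both arms the bias is at most 0.012, and with a flat SD there is none.

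The cost is one sentence and no data. TOEPH has 23 covariance parameters (12 variances and 11 correlations) against 12 for TOEP, so it may also fail to converge, which is why TOEP stays as the last step. The sandwich SE fits less well with small-sample degrees-of-freedom corrections, a minor matter at 300 per arm.
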